14.2 Patient Recruitment - Screening Visit (before treatment start at V1)

- Review and signing of Child Assent and/or Informed Consent Form (ICF)
- Collection of AEs starts after signing ICF
- Demographics and medical history
- Completion of the Inclusion/exclusion checklist by the physician
- Physical examination with specific assessment of hepatosplenomegaly and vital signs (including height)
- Clinical evaluation by the physician using the mAIDAI (Appendix 1)
- Physician Global Assessment (PGA) (Appendix 3)
- Lab testing
 - Genetic evaluations

- Infection evaluations (CMV, EBV, etc.)
- Serology (HIV, HCV, HBV)
- Pregnancy test (UPT and/or hCG as applicable)
- Hematology, clinical chemistry, ESR (at local lab), urinalysis, CRP, Ferritin, TB blood testing (Note: QuantiFERON-TB testing should be done either at central lab or local [hospital] lab, prior to treatment initiation)
- Flow cytometry
- Coagulation (Thrombocytes, Fibrinogen, D-dimer, PTT, PT)
- Specialized lab testing
 - Serum: Total IL-18, free IL-18, IL-18BP

14.3 Baseline visit at Week 0 (V1- Treatment Initiation) – SAOL Phase

- Reassessment of inclusion and exclusion criteria prior to treatment with Tadekinig alfa start
 - Physical examination with specific assessment of hepatosplenomegaly and vital signs
 - Treatment start with Tadekinig alfa
 - Review of AEs and concomitant medications
 - Clinical evaluation by the physician using the mAIDAI
 - Physician Global Assessment (PGA)
 - Patient` s/caregiver`s qualitative evaluation of health status (study specific questionnaire for all patients implemented in protocol version 6)
 - Local Tolerability Index Assessment by Investigator
 - Ophthalmic examination will be performed for the diagnosis (presence/absence), severity and evolution of uveitis and occurrence of ophthalmic adverse events (i.e. toxic neuropathy)
- Lab testing (Samples taken prior to treatment)
 - Hematology, clinical chemistry, ESR (at local lab), urinalysis, CRP, Ferritin,
 - Coagulation (Thrombocytes, Fibrinogen, D-dimer, PTT, PT)
 - Urine pregnancy test, as applicable
- Specialized lab testing
 - Serum: Total IL-18, free IL-18, IL-18BP (Samples taken prior to treatment)
 - Serum: Anti-Tadekinig alfa antibodies (measurement performed on blood drawn before Tadekinig alfa administered for all patients)
 - Additional sample for PK study will be collected at 2 h, 4 h, 6 h and 24h post treatment. Trough levels are calculated based on blood samples used for lab testing (no extra sample needed)
- Treatment initiation

- Two-hour patient observation after first treatment

14.4 Visits at Weeks 1, 2, 3 (V2/Day 7, V3/Day 14, V4/Day 21)

- Physical examination with specific assessment of hepatosplenomegaly and vital signs
- Treatment with Tadekinig alfa (every 2d)
- Review of AEs and concomitant medications
- Clinical evaluation by the physician using the mAIDAI
- Physician Global Assessment (PGA)
- Local Tolerability Index Assessment by Investigator
- Lab testing (Samples taken prior to treatment)
 - Hematology, clinical chemistry, ESR (at local lab), urinalysis, CRP, Ferritin
 - Coagulation (Thrombocytes, Fibrinogen, D-dimer, PTT, PT)
 - Urine pregnancy test, as applicable
- Specialized lab testing
 - Serum: Total IL-18, free IL-18, IL-18BP (Samples taken prior to treatment)
 - Serum: Anti-Tadekinig alfa antibodies (measurement performed on blood drawn before Tadekinig alfa administered for all patients) will be performed at V3

14.5 Visit at Week 4 (V5/Day 28)

- Physical examination with specific assessment of hepatosplenomegaly and vital signs
- Treatment with Tadekinig alfa (every 2d)
- Review of AEs and concomitant medications
- Clinical evaluation by the physician using the mAIDAI
- Physician Global Assessment (PGA)
- Local Tolerability Index Assessment by Investigator
- Lab testing (Samples taken prior to treatment)
 - Hematology, clinical chemistry, ESR (local lab), urinalysis, CRP, Ferritin
 - Coagulation (Thrombocytes, Fibrinogen, D-dimer, PTT, PT)
 - Urine pregnancy test, as applicable
- Specialized lab testing
 - Serum: Total IL-18, free IL-18, IL-18BP (Samples taken prior to treatment)

- Serum: Anti-Tadekinig alfa antibodies (measurement performed on blood drawn before Tadekinig alfa administered for all patients)
- PK assessment - Additional sample for PK study will be collected at 2 h, 4 h, 6 h and 24h post treatment. Trough levels are calculated based on blood samples used for lab testing (no extra sample needed)

14.6 Visits at Week 8, 12 (V6/Day 56, V7/Day 84) – Monthly Visits

- Physical examination with specific assessment of hepatosplenomegaly and vital signs
- Treatment with Tadekinig alfa (every 2d)
- Review of AEs and concomitant medications
- Clinical evaluation by the physician using the mAIDAI
- Physician Global Assessment (PGA)
- Local Tolerability Index Assessment by Investigator
- Lab testing (Samples taken prior to treatment)
 - Hematology, clinical chemistry, ESR, urinalysis, CRP, ferritin
 - Coagulation (Thrombocytes, Fibrinogen, D-dimer, PTT, PT)
 - Urine pregnancy test, as applicable
- Specialized lab testing
 - Serum: Total IL-18, free IL-18, IL-18BP (Samples taken prior to treatment)
 - Serum: Anti-Tadekinig alfa antibodies (measurement performed on blood drawn before Tadekinig alfa administered for all patients) at Week 12 (V7)

14.7 Visit at Week 18 (V8/Day 126): End of SAOL Phase/Start of RW Phase

- Physical examination with specific assessment of hepatosplenomegaly and vital signs
- Review of AEs and concomitant medications
- Clinical evaluation by the physician using the mAIDAI
- Physician Global Assessment (PGA)
- Patient` s/caregiver`s qualitative evaluation of health status
- Local Tolerability Index Assessment by Investigator
- Lab testing (Samples taken prior to treatment)
 - Hematology, clinical chemistry, ESR, urinalysis, CRP, ferritin
 - Coagulation (Thrombocytes, Fibrinogen, D-dimer, PTT, PT)
 - Urine pregnancy test, as applicable
- Specialized lab testing

- Serum: Total IL-18, free IL-18, IL-18BP (Samples taken prior to treatment)
- Serum: Anti-Tadekinig alfa antibodies (measurement performed on blood drawn before Tadekinig alfa or placebo administered for all patients) at Week 18 (V8)
- Treatment with Tadekinig alfa or placebo (every 2 days) as randomized for RW phase
 - **Note:** Study drug administration should occur after all V8 assessments have been performed

14.8 Visits at Weeks 20, 22, 26, 30 (V9/Day 140, V10/Day 154, V11/Day 182, V12/Day 210)

- Physical examination with specific assessment of hepatosplenomegaly and vital signs
- Treatment with Tadekinig alfa or placebo (every 2 days) as randomized for RW phase
- Review of AEs and concomitant medications
- Clinical evaluation by the physician using the mAIDAI
- Physician Global Assessment (PGA)
- Local Tolerability Index Assessment by Investigator
- Lab testing (Samples taken prior to treatment)
 - Hematology, clinical chemistry, ESR, urinalysis, CRP, ferritin
 - Coagulation (Thrombocytes, Fibrinogen, D-dimer, PTT, PT)
 - Urine pregnancy test, as applicable
- Specialized lab testing
 - Serum: Total IL-18, free IL-18, IL-18BP (Samples taken prior to treatment)
 - Serum: Anti-Tadekinig alfa antibodies (only at Weeks 22 (V10) and 26 (V11))

14.9 Study Completion Visit at Week 34 (V13/Day 238)/Study Completion for Patients experiencing disease reactivations during RW/ Early Termination for Discontinued Patients:

- Physical examination with specific assessment of hepatosplenomegaly, vital signs
- Review of AEs and concomitant medications
- Clinical evaluation by the physician using the mAIDAI
- Physician Global Assessment (PGA)
- Patient` s/caregiver` s qualitative evaluation of health status
- Local Tolerability Index Assessment by Investigator
- Lab testing

- Hematology, clinical chemistry, ESR (at local lab), urinalysis, CRP, Ferritin
- Coagulation (Thrombocytes, fibrinogen, D-dimer, PTT, PT)
- Urine pregnancy test, if applicable
- Recording other medications given to the patient after study treatment stop, and if (or not) any response to new medication
- Specialized lab testing
 - Serum: Total IL-18, free IL-18, IL-18BP (Samples taken prior to treatment)
 - Serum: Anti-Tadekinig alfa antibodies

Note: A patient experiencing a partial or full disease reactivation during the 16 week RW phase and thus proceeding to the End of Study Visit will not be considered as having early terminated from the study.

14.10 CLINICAL LABORATORY TESTS

Sample analysis will be performed in the central lab and local labs (as applicable). A list of all samples collected and associated laboratory assessments is provided in **Table 2**. Approximately 10-20 ml of blood will be taken at visits when laboratory tests are required, the actual volume will depend on the patient weight. Due to sample volume limitations duplication of determinations between the central and the local labs will be avoided when possible.

Other clinical laboratory tests may be performed locally by the Investigator, as deemed necessary, to ensure patient safety.

Table 2: Clinical Laboratory Tests

Biochemistry	Haematology
GOT/AST	Hematocrit
GPT/ALT	Haemoglobin
Gamma-glutamyl transferase (GGT)	Red blood cell (RBC) count
	Complete blood count,
	White Blood Cell (WBC) count
Alkaline phosphatase (ALP)	
Total bilirubin	Neutrophils
BUN	Lymphocytes
LDH	Monocytes
Creatinine	Eosinophils
Uric acid	Basophils
Potassium	Platelets
Sodium	MCC
Chloride	MCHC
Calcium	MCV
Total protein	
Serum albumin	Coagulation
Glucose	
Total cholesterol	PT
Triglycerides	PTT, D-Dimer and Fibrinogen
CRP	
ESR (Erythrocyte Sedimentation Rate)	
Viral Infection –	Cytokines and inflammatory mediators
CMV, EBV	IL-18 total
Genetic Analysis –	
Flow Cytometry	IL-18 free
	IL-18BP
Serology	
HIV (anti-HIV1 and anti-HIV2 antibodies, HIV1 Ag)	PK study
Hepatitis C	IL-18BP
Hepatitis B	
Pregnancy Test (UPT and/or hCG as applicable)	Ferritin system
	Ferritin
Urinalysis	
Dipstick: protein, erythrocytes (blood), leukocytes, nitrite, bilirubin, urobilinogen, glucose, ketone bodies, pH, specific gravity	Anti-drug antibodies

15 DATA MANAGEMENT

15.1 Data Collection

- Patient data will be collected on eCRFs and will be substantiated by source documents at the clinical site. Laboratory results from outside laboratories will be received by the site and entered from hard copy print-outs into the eCRF.
- Prior to the start of the study, the Investigator will complete a Registry of Signatures / Delegation of Responsibility Log showing the signatures and handwritten initials of all site staff individuals who are authorised to make or change entries on eCRFs. The eCRFs will be completed according to the eCRF Completion Guidelines (eCCGs) provided by the CRO in writing and/or verbally.
- Data will be collected using, a web-based electronic data capture (EDC) system. The Study Monitor will review all eCRF data to 100% source data verification (SDV) to ensure adequate quality control and complete patient data. Any discrepancies found during the eCRF review will be clarified by the Investigator (or his/her designated staff). This includes eCRF reviews at the site by the Sponsor or its designee, or during quality assurance review of the data or audits.
- The Investigator or designee must record all required patient data using the eCRFs. The Investigator must electronically sign and date a declaration on the eCRF attesting to his/her responsibility for the quality of all data recorded, and that the data represent a complete and accurate record of each patient's participation in the study. All Investigators authorized to approve eCRFs will sign a declaration stating that their handwritten signature is the legal equivalent of an electronic signature. Each patient eCRF will be retained by the Investigator.
- A patient diary will be completed by/for patients dosed at home. The diary does not need to be completed if the patient is hospitalized. The diary may be provided electronically or in hard copy booklets to be completed by the subjects or by another person other than the patient (e.g., Caregiver).
- Data will be collected to the extent possible for subjects who discontinue the treatment. In case of such discontinuation and start of another medication, it is important to capture this information too and also to report whether a response was observed in case of change.
- All DM activities are done according to CRO SOPs.

16 STATISTICS

16.1 General Considerations

The statistical analysis will be conducted by the assigned CRO. Statistical methods will be pre-specified and documented in detail in a Statistical Analysis Plan (SAP) to be finalized before database lock and breaking the treatment blind on all subjects. Any deviations from the analysis pre-planned in the protocol or the SAP will be described and justified in the final study report. All statistical analyses will be generated using validated Base SAS® software, Version 9 or higher.

16.2 Interim Analysis

No interim analysis will be performed at this stage.

16.3 Sample Size Calculations

[figure not shown]
Power Calculations

The primary endpoint of the study is time to first occurrence of disease reactivation (including full and partial disease reactivation) during the RW phase of the study. There is limited historical data for this disease condition, for either a control or an experimental test product, however the frequent recurrence of disease reactivations was expected in the control arm (Wada 2014). Originally, an 8-week event rate was assumed to be 90% and a considerable reduction in disease reactivations for subjects receiving Tadekinig alfa was expected. However, a lower event rate was observed from the currently enrolled (still blinded) patients. Thus, the RW phase is prolonged to a maximum of 16 weeks to better assess the effect of Tadekinig alfa withdrawal. The power calculations below will assume the same 90% event rate in the SOC arm at 16 weeks.

Figure 2 below displays the power achieved for a two-arm study and assumes the following:

- Two-sided log-rank test, with input based on the proportion of patients surviving (i.e., event-free) at 16 weeks;
- Two-sided alpha = 0.05;
- A 1:1 randomization of 10 patients (i.e., 5 patients per arm);
- The proportion of patients surviving (i.e., event-free) in the control arm at Week 16 of the RW phase is 0.1, which equates to a 90% event rate;
- No patients in either group drop out of the study prior to experiencing a disease reactivation or completing the 16-week treatment period as planned;
- Total study time is 32 weeks including a 16 week accrual period and a 16 week follow-up time;
- Varying levels of a hazard ratio, from 0.1 to 0.25 in 0.05 increments.

Figure 2 Power vs. Hazard Ratio

A hazard ratio of 0.1 equates to an assumed 16-week event rate in the Tadekinig alfa group of 20.6% (i.e., a survival event-free rate of 79.4%). These assumptions achieve 78.4% power based on a two-sided log rank test with an overall sample size of 10 subjects to be randomized in the RW phase (5 in the placebo group and 5 in the Tadekinig alfa group). A hazard ratio of 0.1 results in an assumed number of total events among the 10 subjects to be 6.7, with 4.9 occurring in the placebo group and 1.8 occurring in the Tadekinig alfa group.

No power calculations were performed for the SAOL phase of the study, as analysis will be descriptive in nature.

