The figure below displays the power achieved for a two-arm study with a 1:1 randomization of 10 subjects, based on two-sided alpha=0.05, a 16-week event rate of 90% in the control arm, and assumed hazard ratios that vary from 0.1, 0.15, 0.2, and 0.25.

Figure 1: Power vs. Hazard Ratio

A hazard ratio of 0.1 equates to an assumed 16-week event rate in the Tadekinig alfa group of 20.6% (i.e., a survival event-free rate of 79.4%). These assumptions achieve 78.4% power based on a two-sided log rank test with an overall sample size of 10 patients to be randomized in the RW phase (5 in the placebo group and 5 in the Tadekinig alfa group). A hazard ratio of 0.1 results in an assumed number of total events among 10 patients to be 6.7, with 4.9 occurring in the placebo group and 1.8 occurring in the Tadekinig alfa group.

No power calculations were performed for the SAOL phase of the study, as analysis will be descriptive in nature.

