11.2 Study Product Administration

11.2.1 Amount, Dose, Concentration, Frequency

Patients will receive the treatments of r-hIL-18BP at a dose of 2 mg/kg s.c. every 2 days \pm 5 hours for a total treatment period of 18 weeks in the SAOL phase. The maximum dose is 160 mg (note: patients with more than 80 kg body weight will receive the maximum dose of 160 mg).

Patients in the RW phase will be treated with the same dosage or volume (2 mg/kg, s.c. every 2 days) of either Tadekinig alfa or equivalent volume of Placebo as randomized. The treatment period in this phase is up to 16 weeks.

The volume for injection will need to be individually calculated on the basis of the weight of the patient collected at least weekly for patients weighing less or equal to 15 Kg, or in the more recent or current study visit for patients weighing more than 15 Kg. This, corresponds to a dose of 2mg/Kg (or 0.05mL of investigational product per kg patient weight). The required volume will be withdrawn from the vial

using a sterile, single use syringe. Before treatment, the vials will be brought to room temperature (18 – 25°C) by removing them from the refrigerator 15 min prior to administration. The IMP will be withdrawn into a sterile syringe and administered without delay.

Further instructions on IMP handling and storage will be provided by the Sponsor/CRO.

Note: more than 1 vial might be required to deliver the calculated dose.

Drug product selected dose: The safety and tolerability of Tadekinig alfa has been studied in adult human volunteers following single s.c. injections with doses ranging from 20mg to 350mg and repeated s.c. doses (35mg and 175mg) administered on alternate days. In addition, 6 weeks duration Phase Ib studies (three administrations per week) have been completed in Rheumatoid Arthritis (RA) (n=35) subjects and Psoriasis (Pso) (n=36) subjects with doses ranging from 20mg to 160mg in the former, and 20mg to 320mg in the latter. No SAEs were observed in any of the studies and the most frequent AE (mild to moderate) were injection site reactions (with a causality described as “probably related” to Tadekinig alfa).

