During the RW-phase, the reference for a disease reactivation (for the primary endpoint assessment) will be the end of the SAOL phase (V8); for the SAOL phase, reference will be the previous visit, as patients enter the SAOL phase with an active disease.

○ **Partial disease reactivation**

- Increase in the number of affected objective end organ damage categories by at least 2 or
- Increase in the number of affected objective end organ damage categories by at least 1 and worsening of at least 1 systemic inflammatory marker (i.e., serum ferritin levels ≥ 500 ng/mL or serum CRP ≥ 2 x ULN) that was meeting complete response criteria before

○ **Full disease reactivation**

- Increase in the number of affected objective end organ damage categories to at least the number of affected end organ damage categories at baseline (V1) and
- Exacerbation of at least 1 systemic inflammatory marker (i.e., serum ferritin levels ≥ 500 ng/mL or serum CRP ≥ 2 x ULN) that was meeting complete response criteria before

Note: It is recommended that patients suffering from *severe* CNS manifestations are put on rescue immunosuppression treatment.

Time to first occurrence of disease reactivation will be calculated in weeks as the date of disease reactivation during the RW phase minus the date of randomization during the RW phase plus 1, divided by 7. Patients who do not experience a disease reactivation during the RW phase will be censored at the date of their last clinical assessment during the RW phase indicating no disease reactivation. Patients will be assessed for disease reactivation during the RW phase at all scheduled or unscheduled visits.

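### The printed 78.4% power and 6.7 expected events do not fit a 16-week randomised withdrawal phase: the stated event rates give 5.5 events and roughly 70% power

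*Protocol*

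**What the plan says.** Protocol 16.3 assumes a two-sided log-rank test at alpha 0.05, 5 patients per arm, and 10% of placebo patients event-free at RW Week 16. On dropout it says: "No patients in either group drop out of the study prior to experiencing a disease reactivation or completing the 16-week treatment period as planned". On timing it says: "Total study time is 32 weeks including a 16 week accrual period and a 16 week follow-up time".

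For the treated arm, "A hazard ratio of 0.1 equates to an assumed 16-week event rate in the Tadekinig alfa group of 20.6" per cent. The outputs follow: "These assumptions achieve 78.4% power based on a two-sided log rank test with an overall sample size of 10 subjects to be randomized", and an "assumed number of total events among the 10 subjects to be 6.7, with 4.9 occurring in the placebo group and 1.8 occurring" on active drug.

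SAP 7.6 repeats these inputs and outputs. The synopsis repeats the outputs ("total events among 10 patients to be 6.7, with 4.9 occurring in the placebo group and 1.8 occurring in the Tadekinig alfa group") and the event rates, but lists neither the 32-week study time nor the no-dropout assumption.

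Elsewhere, follow-up is limited. Protocol 11.2.1 says of the RW phase: "The treatment period in this phase is up to 16 weeks". SAP 6.4.1.1 says patients without a reactivation "will be censored at the date of their last clinical assessment during the RW phase indicating no disease reactivation". SAP 7.4.2.1 treats event-free completers the same way.

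**The concern.** The 6.7 events cannot be 16-week events at the rates printed beside them. In the Tadekinig alfa arm, 1.8 of 5 is 36%, against a stated 20.6%. In the placebo arm, 4.9 of 5 is 98%, against a stated 90%. Both excesses are what follow-up beyond 16 weeks would produce. An accrual period added to a minimum follow-up describes a trial with a common closing date, in which early entrants are observed longer. In this trial each patient leaves the RW phase at Week 16 whatever the calendar date.

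Power and expected events are the planning figures for the only confirmatory comparison. With so few events, one more or fewer matters. A reader will take 78.4% as close to the customary 80%, which about 70% is not.

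**Working it through.** **Inputs (protocol 16.3).** n = 5 per arm; placebo event-free proportion at 16 weeks 0.10; hazard ratio (HR) 0.1; two-sided alpha 0.05; no dropout; accrual A = 16 and minimum follow-up F = 16 weeks. Exponential event times and uniform accrual are my assumptions.

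**Hazards.** Placebo: λc = ln(10)/16 = 0.1439 per week. Treated: λt = 0.1 × λc = 0.01439. The treated 16-week event rate is 1 − 0.1^0.1 = 20.6%, so the printed rate is right.

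**Expected events.** With fixed follow-up F, events per arm are 5 × [1 − e^(−λF)]. With uniform accrual A, they are 5 × {1 − [e^(−λF) − e^(−λ(A+F))]/(λA)}.

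- *Listed inputs, 16 + 16.* Placebo: 5 × [1 − (0.1 − 0.01)/2.3026] = 4.80. Treated: 5 × [1 − (0.7943 − 0.6310)/0.23026] = 1.45. Total 6.26. The printed 4.9, 1.8 and 6.7 are not returned.
- *The design, 16 weeks for everyone.* 5 × 0.90 + 5 × 0.2057 = 4.50 + 1.03 = 5.53.
- *Accrual 32 + follow-up 16.* Placebo: 5 × [1 − (0.1 − 0.001)/4.6052] = 4.89. Treated: 5 × [1 − (0.7943 − 0.5012)/0.46052] = 1.82. Total 6.71, matching all three printed counts.
- *32 weeks for everyone.* 4.95 + 1.85 = 6.80.

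**Power of the log-rank test at HR 0.1.** Let D be the expected number of events, p the placebo share of those at risk and θ the placebo share of the hazard at each time. Put U = ∫(θ − p)dD, V0 = ∫p(1 − p)dD and V1 = ∫θ(1 − θ)dD. The Lakatos calculation gives Φ(U/√V0 − 1.96) with the null variance, and Φ[(U − 1.96√V0)/√V1] with the alternative variance. The simulation applies the chi-square log-rank test to 5 v 5 patients, 200,000 runs.

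| Follow-up | Events | Lakatos, null variance | Lakatos, alternative variance | Simulated |
|---|---|---|---|---|
| 16 weeks fixed | 5.53 | 68.5% | 72.0% | 70.4% |
| 16 accrual + 16 | 6.26 | 74.6% | 77.2% | 76.3% |
| 32 accrual + 16 | 6.71 | 76.4% | 78.40% | 78.4% |
| 32 weeks fixed | 6.80 | 77.5% | 79.2% | 80.5% |

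Of these four settings, only 32 + 16 reproduces both the printed power and the printed counts. That 32 was entered as the accrual time is an inference from this match; the documents do not show the cause.

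**Size of the drop.** With the same method on both rows: 78.4 − 72.0 = 6.4 points (alternative variance), 76.4 − 68.5 = 7.9 (null variance), 78.4 − 70.4 = 8.0 (simulation). Against the printed 78.4%, the capped values are 6.4 to 9.9 points lower.

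**Other hazard ratios, 16 weeks fixed (null variance / alternative variance / simulated).** HR 0.15: 58.9 / 59.8 / 58.4%. HR 0.20: 49.9 / 49.9 / 48.9%. HR 0.25: 41.9 / 41.7 / 40.6%. The plotted power curves were not visible, so I say nothing about their values.

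**Shorter RW phase for early patients.** SAP 7.4.2.3 refers to patients with a planned 8-week RW phase but gives no number. If 2 or 4 of the 10, split equally between arms, were censored at Week 8 (my assumption), simulated power would be 67.3% or 62.3%.

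**The case against.** The strongest objection is that power depends on the formula, and the documents name the test but no power formula. The Schoenfeld approximation, Φ[√(d/4) × |ln HR| − 1.96], gives 77.2% at d = 5.53, close to 78.4%. That stands as a caveat: the power figure alone is not contradicted by every standard formula. It does not rescue the paragraph. At the printed 6.7 events Schoenfeld gives 84.6%, and 78.4% would correspond to 5.7 events, so it cannot produce the printed pair. At HR 0.1 and 16 weeks it also overstates the simulated power of the named test (77.2% v 70.4%).

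The listed 16 + 16 inputs give 77.2% by the alternative-variance calculation, only 1.2 points from 78.4%. So the claim that the listed inputs fail to return the outputs is firm for the event counts and weak for power.

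No asymptotic figure is exact at 5 v 5. Under the null, the simulated chi-square log-rank test rejects about 7% of the time, so size-corrected power would be lower still.

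Practical consequence is limited. Enrolment is capped at 15 in an ultra-rare disease, no target power is stated, and the plan already discloses a lower blinded event rate than first assumed. The 90% placebo rate matters at least as much: simulated power at 16 weeks and HR 0.1 is about 71%, 63% and 56% at placebo rates of 90%, 80% and 70%. The 8-week figures are hypothetical, and the SAP already has sensitivity analyses for the mixed RW length. All this bears on severity; it does not reconcile the event count.

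**Conclusion.** The concern holds. The event count is the firm part: the stated 16-week rates give 5.53 events (4.50 placebo, 1.03 Tadekinig alfa), not 6.7, whatever power formula is used. The listed 32-week study time cannot apply to patients who leave the RW phase at Week 16, and even if it did it would give 6.26 events.

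Power for the log-rank test at HR 0.1 is about 70% (68.5% to 72.0% by method) rather than 78.4%. This rests on exponential times, no dropout and the plan's own 90% placebo rate. Confidence is high for the events and more moderate for the exact power. The finding does not depend on the 8-week scenarios or on the inferred 32-week accrual entry. It should be fixed, but the validity of the primary analysis does not turn on it.

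**What to change.** Rerun the calculation with every patient's follow-up capped at RW Week 16, and name the power method and software routine. In protocol 16.3 and SAP 7.6, delete or correct the 32-week study-time assumption so that the listed inputs return the printed outputs. In those two sections and the synopsis, restate expected events as about 5.5 (4.5 placebo, 1.0 Tadekinig alfa) and power at HR 0.1 as about 70%, with the value from the named method. Regenerate the power-versus-hazard-ratio figure from the same inputs.

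A useful addition, though not needed for the correction, is one line giving power with the actual number of patients on the 8-week RW phase.

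The cost is text and figure edits in three places. The correction itself changes neither the number of patients nor the analysis. The one downside is a stated power 6 to 10 points lower.
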